5.5.2 Pharmacodynamic, Pharmacogenomic, and Other Biomarker Analyses

Exposure-response Analyses

Following FDA guidance, PK sampling will be conducted in subjects across the pediatric program at regular intervals in order to adequately characterize the PK of eribulin in the pediatric population in the various age cohorts to explore exposure-response (ER) relationships for efficacy and safety (AE). The relationship between exposure to eribulin mesylate and AE or efficacy will be explored graphically and may be modelled if a relationship is deemed to exist.

5.6 Safety Analyses

All safety analyses will be performed on the Safety Analysis Set. Safety data, presented by histology type, will be summarized on an “as treated” basis using descriptive statistics (e.g., n, mean, standard deviation, median, minimum, Q1, Q3 and maximum for continuous variables; n [%] for categorical variables). Safety variables include treatment-emergent adverse events (TEAEs), clinical laboratory parameters, vital signs, 12-lead ECG results, and performance status.

Study Day 1 for all safety analyses is defined as the date of the first dose of study drug.

5.6.1 Extent of Exposure

The number of cycles administered, duration of treatment, number of doses, total dose (mg/m²) per subject, actual dose intensity (mg/m²/week) per subject and relative dose intensity per subject will be summarized for eribulin mesylate and be presented by n, mean with standard deviation, median, minimum, Q1, Q3 and maximum.

Duration of Treatment (weeks) = (Date of first dose of last cycle + 21 - date of first dose of study drug) / 7.

Actual Dose Intensity (mg/m²/week) = Total dose (mg/m²) / Duration of treatment (weeks).

Relative Dose Intensity (%) = Actual Dose intensity (mg/m²/week) / Planned dose intensity * 100, where Planned dose intensity is 0.933 mg/m²/week = 1.4 mg/m² * 2 / 3 weeks.

The number of subjects who had dose changes will be summarized for eribulin mesylate.

5.6.2 Adverse Events

The AE verbatim descriptions (investigator terms from the CRF) will be classified into standardized medical terminology using the Medical Dictionary for Regulatory Activities (MedDRA). Adverse events will be coded to the MedDRA (Version 21.1 or higher) lower level term (LLT) closest to the verbatim term. The linked MedDRA preferred term (PT) and primary system organ class (SOC) will also be captured in the database.

A treatment-emergent adverse event (TEAE) is defined as an AE that emerged during treatment, having been absent at pretreatment (Baseline) or

- Reemerged during treatment, having been present at pretreatment (Baseline) but stopped before treatment, or
- Worsened in severity during treatment relative to the pretreatment state, when the AE was continuous.

Only those AEs that are treatment emergent will be included in summary tables. All AEs, treatment emergent or otherwise, will be presented in subject data listings.

The TEAEs will be summarized by histology group. The incidence of TEAEs will be reported as the number (percentage) of subjects with TEAEs by SOC and PT. A subject will be counted only once within a SOC and PT, even if the subject experienced more than 1 TEAE within a specific SOC and PT. The number (percentage) of subjects with TEAEs will also be summarized by highest Common Terminology Criteria for Adverse Events (CTCAE) V4.03 grade.

The number (percentage) of subjects with TEAEs will also be summarized by relationship to study drug (Yes [related] and No [not related]).

The number (percentage) of subjects with TEAEs with fatal outcomes will be summarized by MedDRA SOC and PT for each histology type. A subject data listing of all AEs with fatal outcomes will be provided.

The number (percentage) of subjects with treatment-emergent serious adverse events (SAEs) will be summarized by MedDRA SOC and PT for each histology type. A subject data listing of all SAEs was provided.

The number (percentage) of subjects with TEAEs leading to discontinuation from study drug will be summarized by MedDRA SOC and PT for each histology type. A subject data listing of all AEs leading to discontinuation from study drug will be provided.

5.6.3 Laboratory Values

Laboratory results will be summarized using Système International (SI) units, as appropriate. For all hematology and chemistry parameters listed in the protocol Section 9.5.1.6.3 (Table 8), the actual value and the change from baseline to each post-baseline visit will be summarized using descriptive statistics (n, mean, standard deviation, median, Q1, Q3, minimum, maximum).

Laboratory test results will be assigned a classification according to CTCAE grade (Appendix 1 in the protocol). Shifts of CTCAE grade from baseline to worst post-baseline will be presented. Percentages will be based on the number of subjects with both non-missing baseline and at least one post-baseline result for relevant parameters.

Urinalysis and pregnancy test data will be listed.

5.6.4 Vital Signs

Descriptive statistics for vital signs parameters (i.e., systolic and diastolic blood pressure (BP), pulse, temperature, weight, and height) and changes from baseline will be presented by visit.

A listing of all vital sign measurements will be provided.

5.6.5 Electrocardiograms

ECG assessments will be performed. QT intervals will be measured from Lead II and will be corrected for heart rate (QTc) using Fridericia's (QTcF) and Bazett's (QTcB) correction factors. The primary QTc parameter will be QTcF. Secondary parameters will be QTcB, QT, QRS, and heart rate.

Shift tables will present shifts from baseline to end of treatment in ECG interpretation (categorized as normal; abnormal, not clinically significant; and abnormal, clinically significant).

In addition, the number and percentage of subjects with at least 1 post-baseline abnormal ECG result in QTc Fridericia and Bazett's during the treatment period will be summarized. Clinically abnormal ECG results in QTc Fridericia and Bazett's will be categorized as follows:

Absolute QTc interval prolongation:

- QTc interval >450 ms
- QTc interval >480 ms
- QTc interval >500 ms

Change from baseline in QTc interval:

- QTc interval increase from baseline >30 ms
- QTc interval increase from baseline >60 ms

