- Males who have not had a successful vasectomy (confirmed azoospermia) or if they and their female partners do not meet the criteria above (ie, not of childbearing potential or practicing highly effective contraception throughout the study period or for 3 months after study drug discontinuation). No sperm donation is allowed during the study period or for 3 months after study drug discontinuation.

2. Concomitant medications:

- Corticosteroids: Subjects receiving corticosteroids who have not been on a stable or decreasing dose of corticosteroid for at least 7 days prior to study drug administration (except when indicated for Central Nervous System (CNS) metastases, then subjects must not have received corticosteroids for at least 28 days).
- Anticancer Agents: Subjects who are currently receiving other anticancer agents.
- Anti-GVHD agents post-transplant: Subjects who are receiving cyclosporine, tacrolimus or other agents to prevent graft-versus-host disease post bone marrow transplant.
- Strong CYP3A4 inducers/inhibitors (See [Section 9.4.6.1.1](#), Drug-Drug Interactions).

3. Received prior therapy with eribulin mesylate.

4. Any other malignancy that required treatment (except for non-melanoma skin cancer, or histologically confirmed complete excision of carcinoma in situ), within 2 years prior to study drug administration.

5. Has hypersensitivity to eribulin or any of the excipients.

6. Has a prior history* of viral hepatitis (B or C) as demonstrated by positive serology (presence of antigens) or have an uncontrolled infection requiring treatment (* Subjects with a known prior history of hepatitis B or C may be eligible pending agreement with the sponsor).
7. Has > Grade 1 peripheral sensory neuropathy or > Grade 1 peripheral motor neuropathy graded according to the Modified (“Balis”) Pediatric Scale of Peripheral Neuropathies.
8. Has cardiac pathology:
 - Subjects with known congestive heart failure, symptomatic or left ventricular (LV) ejection fraction <50% or shortening fraction <27%
 - Subjects with congenital long QT syndrome, bradyarrhythmias, or QTc >480 msec on at least 2 separate ECGs.

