ECG monitoring to evaluate RR, PR, QRS, and QT intervals and QTc interval (corrected for heart rate [QTc] using Fridericia's [QTcF] and Bazett's [QTcB] correction factors) at pre-study, during Cycle 1 (pre- and post-infusion Day 1 and Day 8) and as clinically indicated during subsequent cycles and during follow-up (28 days after the last dose of drug).

A full neurological examination will be conducted at Screening. On subsequent cycles an assessment of neuropathy (neuropathy present/absent and CTC AE Grade) will be assessed as part of the physical examination

Bioanalytical Methods

Plasma concentrations of eribulin mesylate will be determined using a validated liquid chromatography coupled with tandem mass spectrometry (LC-MS/MS) method. The lower limit of quantification (LLOQ) is 0.2 ng/mL.

Statistical Methods

Study Endpoints

Primary Endpoints

- Objective response: number of subjects achieving a best objective response of partial or complete response (PR or CR), by up to 24 weeks after all subjects have completed response assessment. Response assessment will be as determined by investigator.

Secondary Endpoints

- PFS: defined as the time from the first dose date to the date of disease progression or date of death (whichever occurs first).
- Safety and tolerability: AEs, SAEs, clinical laboratory values, ECG parameters, vital sign measurements, and performance status.
- DOR: defined as the time from the first date of documented PR or CR to the date of disease progression or date of death (whichever occurs first).
- OS: defined as the time from the first dose date to the date of death.

Exploratory Endpoints

- Exposure of eribulin mesylate.

Analysis Sets

Full Analysis Set (FAS) will consist of all subjects who receive at least 1 dose of study drug.

Safety Analysis Set (SAS) will consist of all subjects who receive at least 1 dose of study drug.

Pharmacokinetic Analysis Set (PAS) will include subjects who have at least 1 evaluable plasma concentration and sufficient dosing information.

Efficacy Analyses

The primary analysis will be based on investigator assessments of tumor response.

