Adverse events		Throughout													X	
Survival status															X ^m	X ^o

BSA = body surface area, CT = computed tomography, ECG = electrocardiogram, EOT = end of treatment, MRI = magnetic resonance imaging.

- a. The Screening Period extends from Day -28 to Day -1. Day -28 to -1, computed tomography (CT) / magnetic resonance imaging (MRI) scans must be performed within 28 days prior to study drug administration. For logistical purposes, informed consent may be obtained from Day -29. All clinical and laboratory studies to determine eligibility must be performed **within 7 days prior to study drug administration** unless otherwise indicated. Laboratory values used to assess eligibility must be no older than 7 days at the start of therapy.
- b. Assessments/procedures may be obtained within 72 hours prior to the start of the subsequent cycle.
- c. Vital signs should be performed Day 1, Day 8, and at the End of Treatment (EOT) for subjects receiving eribulin mesylate.
- d. Height should be measured every other cycle from Cycle 3.
- e. Performance status will be measured using Karnofsky or Lansky scales.
- f. Female subjects of childbearing potential require a negative urine or serum (depending on local practice) pregnancy test prior to starting treatment (within 72 hours prior to Cycle 1 Day 1).
- g. Subjects will need to have hematology samples obtained weekly; an outside complete blood count can be performed when at the physician's discretion.
- h. PK sample collection schedule:
 1. Immediately post- eribulin infusion on Day1 of each cycle for the first 3 cycles
 2. Pre- eribulin infusion and immediately post-infusion on Day 8 of each cycle for the first 3 cycles.
- i. On Days 1 and 8 of Cycle 1, two 12-lead ECGs will be obtained: one 15-30 minutes before infusion and a second one immediately after the infusion. The post-infusion ECG should precede the collection of the post-infusion PK sample on Days 1 and 8 of Cycle 1.

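### SAP 5.6.5 shifts ECG interpretation to an undefined end of treatment rather than to the worst post-baseline tracing, and its absolute QTc rows do not separate children already above the threshold at baseline

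*SAP*

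**What the plan says.** **Interpretation.** SAP 5.6.5 and Protocol 9.7.1.8.5 classify each ECG as normal, abnormal but not clinically significant, or abnormal and clinically significant. The planned display is: "Shift tables will present shifts from baseline to end of treatment in ECG interpretation". Neither section defines end of treatment for ECGs.

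**QTc.** SAP 5.6.5 then summarises "the number and percentage of subjects with at least 1 post-baseline abnormal ECG result in QTc Fridericia" (and Bazett) over the treatment period. The absolute categories are above 450, 480 and 500 ms, with no condition on the baseline value. The change categories are rises of more than 30 ms and more than 60 ms, the latter worded "QTc interval increase from baseline >60 ms".

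**Schedule.** Protocol Table 9 has an ECG at screening and at the EOT visit. Its footnote i adds: "On Days 1 and 8 of Cycle 1, two 12-lead ECGs will be obtained", one before and one after infusion. Later cycles have ECGs only when clinically indicated. The Protocol Synopsis also mentions ECGs "during follow-up (28 days after the last dose of drug").

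**Eligibility.** Exclusion criterion 8 removes children with "bradyarrhythmias, or QTc >480 msec on at least 2 separate ECGs".

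**Other shift tables in the same SAP.** For laboratory data, section 5.6.3 states: "Shifts of CTCAE grade from baseline to worst post-baseline will be presented". Section 5.6.6 does the same for Karnofsky and Lansky scores.

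**The concern.** A shift table is there to show deterioration on treatment. One that compares baseline with a single late tracing can report no change for a child whose ECG was clinically significantly abnormal in Cycle 1 and then recovered. The SAP avoids this for laboratory grades and performance status and gives no reason for treating ECGs differently.

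The absolute QTc rows have a different weakness. A child at 460 ms before and after dosing is counted in the row above 450 ms although nothing changed. A reader of that row cannot tell new prolongation from prolongation present at entry.

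ECG parameters are part of the secondary safety endpoint, and Protocol 9.4.1.1.1 has its own instructions on QTc prolongation, so these tables will be read. With about 15 children per histology, one child visibly moves a percentage.

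**Working it through.** The plan gives no ECG rate, so there is no figure to reproduce. The check is a count of tracings, followed by arithmetic on the QTc rows.

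**1. What the shift table can see.** Six ECGs are scheduled per child: screening, four in Cycle 1 and EOT. The Day 1 pre-infusion tracing precedes the first dose. Three Cycle 1 tracings follow it: Day 1 post-infusion, Day 8 pre-infusion and Day 8 post-infusion.

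| Meaning of end of treatment | Source | Tracing used if no unscheduled ECG | Post-dose Cycle 1 tracings left out |
|---|---|---|---|
| EOT visit, within 28 days after last dose | Protocol 9.5.1.2 and Table 9 | EOT | All 3 |
| Last on-treatment value | Protocol 9.7.1.8.3, laboratory data only | Day 8 post-infusion | 2 of 3 |

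The two readings give different tables, and neither shows the worst tracing. A clinically significant Day 1 post-infusion finding that has resolved by Day 8 and stays resolved is missing from both.

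**2. Who can be in the row above 450 ms without any change.** The exclusion requires more than 480 ms on at least two ECGs, so 451 to 480 ms at entry is allowed. The rows above 480 and 500 ms are less exposed: a child could start above those limits only through a single high tracing or through the other correction formula.

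**3. Weight of one such child.** 1/45 = 2.2 percentage points overall; 1/15 = 6.7 points in a cohort.

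**4. Illustration with assumed rates.** Let p0 be the share above 450 ms at baseline and again afterwards, and q the incidence among the rest. The documents give neither.

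- Reported = p0 + (1 − p0)q
- New = (1 − p0)q
- Pre-existing share of the count = p0 / reported
- Chance of at least one such child among 45 = 1 − (1 − p0)^45

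| p0 | q | Reported | New | Pre-existing share | Chance of at least 1 in 45 |
|---|---|---|---|---|---|
| 2% | 10% | 11.8% | 9.8% | 17% | 0.60 |
| 5% | 5% | 9.8% | 4.8% | 51% | 0.90 |
| 10% | 5% | 14.5% | 4.5% | 69% | 0.99 |

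**5. Simulation with no drug effect.** Assumed: true QTcF normal with between-child SD 18 ms, each tracing adding error with SD 10 ms, baseline capped at 480 ms, and the maximum of four post-baseline tracings (three post-dose in Cycle 1, plus EOT). The cap is a simplification of the two-ECG exclusion rule.

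| Assumed mean | Any above 450 ms | New crossings | Already above at baseline (difference) | Difference × 45 | Share of count |
|---|---|---|---|---|---|
| 410 ms | 6.2% | 4.4% | 1.8% | 0.8 children | 29% |
| 420 ms | 15.2% | 9.7% | 5.5% | 2.5 children | 36% |
| 430 ms | 30.2% | 16.7% | 13.5% | 6.1 children | 45% |

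At an assumed mean of 400 ms, only about 0.2 of 45 children would be pre-existing. At every mean shown, more than half of the count consists of new crossings produced by measurement variation alone.

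**The case against.** A reader might infer that on-drug QTc changes are hidden. The documents do not support that. The QTc counts use any post-baseline value in the treatment period, so an abnormal Day 8 QTc that later normalises is counted. The rows for rises of more than 30 and 60 ms are adjusted for baseline by construction, and a child steady at 460 ms does not enter them. The Protocol Synopsis adds summaries of ECG parameters with change from baseline, and a listing of treatment-emergent ECG abnormalities. Protocol 9.5.1.6.1 makes a QTc above 450 ms with a rise above 60 ms an adverse event (unless it is already part of a reported clinical symptom) and asks for any other ECG abnormality that the investigator regards as one. All of this stands, and it confines the shift-table gap to transient changes other than QTc.

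A reader might also take it as settled that the end-of-treatment tracing comes up to 28 days after the last dose. That is one of two readings.

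Finally, the simulation rests on assumed means and SDs, and most of its crossings would remain after the change. That also stands. The listings and adverse-event reports do not close the remaining gap: they do not give a count by histology of children whose interpretation worsened, and QTc thresholds do not register rhythm or conduction findings.

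**Conclusion.** The point holds in a narrow form. The interpretation shift can miss a transient, clinically significant change in Cycle 1, depends on an undefined term, and departs from the SAP's own worst-post-baseline convention. The absolute QTc rows, mainly the one above 450 ms, mix pre-existing with new prolongation.

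The firm size is 2.2 points per affected child among 45 and 6.7 points in a cohort of 15. How many children would be affected depends on baseline QTc values that the documents do not give; under the simulated means of 410 to 430 ms it is about 0.8 to 6.1 of 45. The rows for change from baseline are unaffected. No primary endpoint, sample size or decision rule is involved. This is a cheap improvement to a descriptive safety table.

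**What to change.** In SAP 5.6.5:

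1. Define baseline, treatment period and end of treatment for ECGs. For baseline, say whether it is the screening or the Day 1 pre-infusion tracing.
2. Shift ECG interpretation from baseline to worst post-baseline. Keep end of treatment, as defined, as an optional extra column.
3. Tabulate worst post-baseline QTc category by baseline category (450 or below, above 450 to 480, above 480 to 500, above 500 ms). Alternatively, report each threshold among children at or below it at baseline, next to the existing counts.
4. Leave the rows for rises of more than 30 and 60 ms as they are.

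The cost is SAP wording, minor programming and one extra table; no new data are needed. The change will not remove threshold crossings caused by measurement noise, so the new-crossing counts should not be read as drug effect on their own.

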5.6.6 Other Safety Analyses

The changes of Karnofsky and Lansky performance status scores from baseline to worst post-baseline will be presented in shift tables.

5.7 Other Analyses

Not applicable.

5.8 Exploratory Analyses

Exploratory analyses may be conducted as appropriate. Any exploratory analyses that are performed will be appropriately titled and labeled as exploratory and will be clearly distinguished from planned analyses when results are reported in the Clinical Study Report.

6 INTERIM ANALYSES

Data will be monitored on an ongoing basis; depending on evaluation by the investigators and sponsor, if sufficient responses (PR or CR) are observed, then this histology type will be recommended for inclusion in the subsequent study.

7 CHANGES IN THE PLANNED ANALYSES

Not applicable.

8 DEFINITIONS AND CONVENTIONS FOR DATA HANDLING

Censoring Rules for PFS/DOR

The PFS censoring rules in this SAP and definition of progression date follow the Food and Drug Administration (FDA) “Guidance for Industry Clinical Trial Endpoints for the Approval of Cancer Drugs and Biologics (2007)”.

Table 1 Censoring Rules for Progression-free Survival Endpoint

Situation	End Date	Censored
Investigator documented PD	Date of the first assessment of the series of radiologic tests that determined PD	No
Death during the study before first PD	Date of death	No
No baseline or post-baseline tumor assessments	Date of first dose	Yes
No progression and no death at the time of data cutoff	Date of last adequate tumor assessment* prior to data cutoff	Yes
Non-study anticancer treatment initiated before progression or death	Date of last adequate tumor assessment* prior to or on date of non-study anticancer treatment	Yes
Death or progression after more than one missed tumor assessments**	Date of last adequate tumor assessment* prior to missed tumor assessments	Yes

PD = progressive disease.

* Adequate tumor assessment is radiologic assessment of CR, PR, SD, non-CR/non-PD or PD as determined by investigators at regular interval as defined in the protocol. Any tumor assessments after new anticancer treatment starts will be removed in the definition of PFS.

**More than one missed visit/adequate tumor assessment is defined as having the duration between the last adequate tumor assessment and PD or death being longer than the gap limit.

a) The gap from baseline to the 1st assessment post-baseline (calculated from C1D1), gap limit = 2*6 weeks + 2*3 Days = 90 days.

- b) The gap from the 1st assessment post-baseline, or from any later assessment -- call it "previous assessment", to the next assessment.
- if Study Day of the previous assessment < (18 weeks - 3 days), then gap limit = 2*6 weeks + 2*3 days = 90 days;
 - if (18 weeks - 3 days) <= Study Day of the previous assessment < 24 weeks - 3 days, then gap limit = 6 weeks + 9 weeks + 2*3 days = 111 days;
 - if Study Day of the previous assessment >= 24 weeks - 3 days, the gap limit = 2*9 weeks + 2*3 days = 132 days.

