9.5.1.3.2 SECONDARY

Efficacy will also be evaluated according to a secondary endpoint (PFS; defined as the time from the date of the first dose of study treatment until the date of first documentation of progressive disease (PD) or date of death [whichever occurs first]). Assessments for these endpoints are to be performed every 6 weeks by use of consistent imaging methodology (ie, CT scan/MRI or bone scan) and consistent use or nonuse of contrast media) until Week 24, then every 9 weeks. In addition, OS status (disposition) and DOR will be assessed throughout the study. For subjects receiving radiotherapy and/or surgery for local control post week 24, progression will be assessed as the date of radiotherapy/surgical procedure.

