9.7.1.1.2 SECONDARY ENDPOINTS

The secondary endpoints are:

- PFS: defined as the time from the first dose date to the date of disease progression or date of death (whichever occurs first).
- Safety and tolerability: AEs, SAEs, clinical laboratory values, ECG parameters, vital sign measurements, and performance status.
- DOR: defined as the time from the first date of documented PR or CR to the date of disease progression or date of death (whichever occurs first).
- OS: defined as the time from the first dose date to the date of death.

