5.4.2 Secondary Efficacy Analyses

The secondary analyses will be to estimate the PFS, DOR, and OS in all cohorts combined. Median PFS, DOR, and OS with the corresponding 95% confidence intervals (CI) will be estimated using Kaplan-Meier method (Kaplan; Meier. 1958). Descriptive statistics will be provided. Duration of response (DOR) will be calculated for subjects with an objective response of PR or CR.

Censoring rules for PFS/DOR are listed in [section 8](#): definitions and conventions for data handling. For OS, subjects who were alive at the data cutoff date will be censored at the data cutoff date, and subjects who were lost to follow-up, withdrew consent, or had survival status collected as “Study terminated by Sponsor” will be censored at the date the subject was last known to be alive.

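### The protocol counts local-control radiotherapy or surgery after Week 24 as progression on the procedure date; SAP Table 1, used for PFS and DOR, has no such event, and the SAP declares no change

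*SAP*

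**What the plan says.** Protocol 9.5.1.3.2, the paragraph that covers PFS and mentions DOR and OS, states: "For subjects receiving radiotherapy and/or surgery for local control post week 24, progression will be assessed as the date of radiotherapy/surgical procedure". Protocol 9.4.6 allows radiotherapy for local control from Week 24 with study drug continuing, so the situation is foreseen. It does not mention surgery.

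SAP 5.4.2 says "Censoring rules for PFS/DOR are listed in" Section 8, so one table governs both endpoints. Table 1 there has two event rows. Investigator-documented PD is dated "Date of the first assessment of the series of radiologic tests that determined PD", and death is dated at death. The other four rows censor. The one nearest to local control, for non-study anticancer treatment started before progression or death, sets the end date at "Date of last adequate tumor assessment* prior to or on date of non-study anticancer treatment". A footnote adds: "Any tumor assessments after new anticancer treatment starts will be removed in the definition of PFS". Section 8 also says that its censoring rules and progression date follow a named FDA guidance.

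The endpoint definitions in Protocol 9.7.1.1.2 and SAP 5.1.2 agree with each other, and neither contains the local-control rule. SAP Section 7, on changes in the planned analyses, reads "Not applicable".

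**The concern.** The endpoint definitions leave the date of disease progression open. The protocol fills the gap in one way for local control after Week 24, and the SAP table fills it in another. The SAP is also ambiguous in itself, because neither *non-study anticancer treatment* nor *new anticancer treatment* is defined. Two analysts with the same data could therefore report different PFS tails beyond Week 24 and different median DORs.

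DOR is the more exposed endpoint. Few responders are expected, and they are the subjects most likely to be progression-free at Week 24 and so to be candidates for local control. The trial is open-label, so the choice should not be left until the data have been seen.

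**Working it through.** **Text comparison.** Take a subject who is progression-free at the Week 24 scan and has local control at Week 26.

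- Protocol 9.5.1.3.2: event at Week 26.
- SAP reading 1, local control is non-study anticancer treatment: censored at the Week 24 scan, later scans removed.
- SAP reading 2, it is not: at risk until radiologic PD or death.
- SAP reading 3, the investigator records PD because of 9.5.1.3.2: an event, but the row ties its date to radiologic tests, so perhaps Week 24 or Week 33.

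No SAP reading clearly gives an event at Week 26. The plan states no figure that depends on this rule, and the sample size was not calculated statistically, so there is no plan figure to reproduce. What follows is illustration.

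**PFS.** Inputs: N = 45; median PFS 2.9 months, assumed from the adult adipocytic subgroup in Protocol 7.1.3.2; exponential times.

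- Week 24 = 168/30.4375 = 5.52 months.
- Progression-free at Week 24: 45 × 2^(−5.52/2.9) = 45 × 0.267 ≈ 12.
- If one third of these (4) have local control, PFS just before the Week 33 scan is 8/45 = 17.8% under the protocol and 12/45 = 26.7% if they are censored or kept at risk.
- In 3,000 simulated trials, 12-month PFS is 4.1% (protocol), 6.2% (censored) and 6.1% (at risk). Median PFS differs in 0% of trials, or in 5% to 6% if the assumed median is 4.0 months. In fixed-quantile examples the median moves only when the assumed median lies beyond about Week 24: with 32 to 40 weeks it is 26 weeks under the protocol and 33 to 42 weeks otherwise.

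**Number of responders.** The documents give no pediatric response rate for eribulin. Two rates from other settings give 45 × 2/32 = 2.8 (adult adipocytic sarcoma, Protocol 7.1.3.2) and 45 × 8% = 3.6 (another drug class in Ewing sarcoma, Protocol 7.1.1.3). Values of 3 to 5 are therefore shown.

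**DOR by hand, 3 responders.** First response at Week 6; PD scans at Weeks 18, 33 and 42; the second subject has local control at Week 26.

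| Handling | Durations in weeks (+ = censored) | Kaplan-Meier steps | Median |
|---|---|---|---|
| Protocol | 12, 20, 36 | 0.667, 0.333, 0 | 20 |
| Censored at Week 24 | 12, 18+, 36 | 0.667, 0 | 36 |
| At risk to PD | 12, 27, 36 | 0.667, 0.333, 0 | 27 |
| PD dated Week 24 or Week 33 | 12, 18 or 27, 36 | 0.667, 0.333, 0 | 18 or 27 |

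**DOR by simulation.** 8,000 trials per cell. Assumptions: first response at Week 6 (70%) or Week 12 (30%); exponential DOR; scans at Weeks 6, 12, 18 and 24, then every 9 weeks; local control in a fixed share of those PD-free at Week 24, spread evenly over the next 6 weeks. The base case is a 6-month DOR median and a one-third share. The range covers medians of 4 to 8 months and shares of 1/6 to 1/2.

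| Responders | Censored median longer than protocol, base case | Range |
|---|---|---|
| 3 | 30% | 12% to 49% |
| 4 | 42% | 16% to 64% |
| 5 | 52% | 23% to 74% |

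The censored median is shorter in under 1% of trials. With 3 responders, the at-risk median is longer in 39% (16% to 61%). Under reading 3 the median differs in 31% (Week 24 date) or 33% (Week 33 date), by at most 6 or 9 weeks. Requiring confirmed response changes the 3-responder figure little: 32% (14% to 50%).

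Lower inputs shrink the effect. With 3 responders, a 3-month DOR median and local control in 5%, 10% or 1/6, the censored median is longer in about 2%, 6% and 9% of trials. With a 2-month median it is longer in about 2% to 5%.

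**The case against.** The case for leaving this as a minor clarification has several parts.

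- *The sentence is not in the statistics section.* It stands under efficacy assessments, the formal endpoint definitions match, and Protocol 9.7.1 leaves further detail to the SAP, so SAP Section 7 may be accurate. This is fair as to Section 7 alone. But the sentence fixes a progression date for PFS, and the SAP table does not carry it. Adding detail does not cover dropping an explicit event rule.
- *It may instruct the assessor.* PD would then be recorded and enter the first row of Table 1 as an event. This is plausible, and the gap then shrinks to a dating difference of at most 6 or 9 weeks. The row still ties the date to radiologic tests, so the procedure date is lost.
- *Radiotherapy that the protocol permits is hardly non-study treatment.* This weakens the censoring reading for radiotherapy, though not for surgery. It leaves the at-risk reading, which also departs from the protocol.
- *The SAP cites a guidance.* The departure may be deliberate. If so, it should be declared.
- *The programming specifications may settle it.* SAP Section 9 places them in separate documents, which are not available here. Whether a subject is an event or censored belongs in the SAP.
- *The size is hypothetical and no decision depends on it.* This stands. With short responses and rare local control the effect is a few percent of trials, and a median DOR from 3 or 4 responders is imprecise under any rule.

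**Conclusion.** The two documents disagree, and the SAP does not determine the handling. That follows from the text alone and needs no assumption. It should be fixed, but it does not threaten the main result: the count of confirmed responders does not use Table 1, and median PFS is essentially unchanged unless it lies near or beyond Week 24.

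The exposed results are the PFS tail after Week 24 and median DOR. Under the base assumptions, censoring lengthens median DOR relative to the protocol rule in 30% to 52% of trials with 3 to 5 responders, and almost never shortens it. With shorter responses and rarer local control the share falls to a few percent. All these percentages depend on assumed local-control rates and response durations.

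**What to change.** Before database lock, choose one of two routes.

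1. Add a row to SAP Table 1 for PFS and DOR: local-control radiotherapy or surgery after Week 24 and before PD; end date, the procedure; not censored. Run the censored version as a named sensitivity analysis.
2. Keep the SAP rule as the main analysis, amend Protocol 9.5.1.3.2, record the departure in SAP Section 7, and run the procedure-date rule as the sensitivity analysis.

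Under either route:

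- Define non-study and new anticancer treatment, and say whether local-control radiotherapy and surgery are included.
- State how investigator-documented PD is dated when no radiologic test determined it.
- Align the time boundary: 9.4.6 speaks of radiotherapy from Week 24, 9.5.1.3.2 of procedures after it.
- Address a neighboring conflict: Protocol 9.4.6.2 judges other antitumor therapy to be evidence of progression, while Table 1 censors it.
- Reconcile the protocol passages on concomitant therapy. The Synopsis lacks the Week 24 exception for radiotherapy that 9.4.6 and 9.4.6.2 carry.

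The cost is one table row, one definition, and one extra Kaplan-Meier run each for PFS and DOR. Protocol 9.4.6 has malignancy-related procedures recorded, but nothing shows that local-control intent is captured, so check the CRF. Route 1 has a drawback: it counts subjects without radiologic PD as progressed, so the PFS tail and median DOR will almost always be equal to or shorter than under the SAP rule. The sensitivity analysis makes that visible.
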